### 6.1 Study Visit Procedures

A written, signed informed consent form (ICF) must be obtained from each subject prior to performing any study procedure. Medical/surgical history, medication record (prior and concomitant medications and therapy), and a physical examination including vitals will be obtained for all subjects at the Screening Visit. A series of laboratory and diagnostic/clinical tests and evaluations will be performed. At least two visits to the clinical facility may be necessary to complete all screening procedures, including an endoscopy. The endoscopy should be performed after all other eligibility criteria have been met and within 28-5 days of randomization to allow 3-component Modified Mayo score calculation.

Subjects may be re-screened one time at the discretion of the Sponsor if they fail their initial screening.

For Cohort 2 - the first screening test after informed consent has been obtained should be buccal swab for CDx status identification, unless already known from study PR100-105 (global sample collection study). If the buccal swab testing shows a result of CDx+, the subject may complete all other screening procedures as per [Table 1](#). If the buccal swab is CDx- the subject will be screen failed. The 35-day screening window additional study assessments need not begin until the first study assessment post ICF and CDx status is obtained.

After randomization, all subjects will be evaluated frequently through a series of physical examinations, and laboratory tests and assessments for safety and efficacy as described in the Schedule of Study Assessments tables ([Section 6.1.1](#)).

## 6.1.1 Schedule of Study Assessments

**Table 1 Schedule of Study Assessments – Screening Period**

Procedure	Study Visit Screening	NOTES
		Screening duration is up to 35 days (5 weeks) *NOTE: for Cohort 2, the 35-day window should start after informed consent and CDx status is known
Eligibility Assessments		
Informed Consent	X	
Inclusion/Exclusion Criteria	X	
Medical and Surgical History	X	
Smoking History	X	
Prior and Current Concomitant Medications	X	
Safety Assessments		
Complete Physical Examination	X	
Interim Physical Examination		
Vital Signs	X	Including height and weight
ECG	X	
Chest X-Ray	X	Must be performed within 6 months of the screening visit with documentation on file.
Adverse Events Assessment	X	
Subject training on electronic diary (eDiary) completion	X	
Issue eDiary to subject	X	
Endoscopy with biopsy	X	Endoscopy should be performed between 28 to 6 days prior to the Week 0/Day 1 visit. Note that subject will need at least 3 consecutive evaluable days or 4 non-consecutive evaluable days of symptoms before Day 1. For subjects who have not had a screening colonoscopy for malignancy per local guideline, a surveillance colonoscopy should be performed. Refer to Section 6.4.2 . Endoscopy should be performed after all other eligibility criteria have been met.
Laboratory Tests		
Pharmacogenomics (buccal swab and blood)	X	For Cohort 2, a buccal swab should be collected and result obtained before all other screening assessments, unless CDx status already known from Study PR100-105
Stool PCR or Culture	X	Can be performed centrally or locally. Ova and parasite examination should also be performed based on local guidelines.
C. difficile PCR/Toxin	X	Can be performed centrally or locally.
Fecal calprotectin	X	To be performed during screening, prior to Week 0/Day 1
CBC	X	
Chemistry Panel	X	
hsCRP	X	
Urinalysis	X	
QuantiFERON-TB	X	Should be repeated if result indeterminate. If indeterminate twice, then either screen fail or be considered for treatment for latent TB, unless deemed not necessary by infectious disease or pulmonary

Procedure	Study Visit Screening	NOTES Screening duration is up to 35 days (5 weeks) *NOTE: for Cohort 2, the 35-day window should start after informed consent and CDx status is known
		specialist. No need to test if negative result available within 90 days of screening.
HbsAg, HbcAb, and HCV Ab	X	If HCV Ab positive, confirmation by undetectable HCV RNA. If HbcAb is positive and Hep B sAg negative, Hep B DNA will be done as reflexive test, and if undetectable, then not exclusionary. No need to test if negative result available within 90 days of screening.
Human Immunodeficiency Virus (HIV)	X	Per local regulations. To be assayed centrally or locally per country/regional regulations. Confirmation and documentation of a negative HIV test result within 3 months (except for subjects in Czech Republic) prior to screening will be accepted.
Serum Pregnancy Test (WOCBP only)	X	

**Table 2 Schedule of Study Assessments – Induction Period**

	Study Week	Study Visit							Early Termination	NOTES
		0	2	6	10	12	85			
	Study Day	1	15	43	71	85				
	Visit window (days)	0	±3	±3	±3	±3				
Procedure										
Eligibility Confirmation	X									
Randomization	X								Via IRT system	
Complete Physical Examination						X		X		
Targeted Physical Examination	X	X	X	X	X					
Vital Signs	X a	X	X	X	X	X a		X	Heart rate, temperature, blood pressure; Take pre-dose (no more than 30 minutes pre-infusion), end of infusion, and end of observation period a Weight needed	
ECG	X					X		X		
Adverse Events Assessment	X	X	X	X	X	X		X		
Concomitant Medication	X	X	X	X	X	X		X		
Efficacy Assessments										
Endoscopy with Biopsy						X		X	Endoscopy to be performed 7 or 6 days prior to or within +3 days after the Week 12 visit, or at the early termination visit. Refer to Section 6.4.2.	
Review eDiary Data from Subjects	X	X	X	X	X	X		X	Remind subjects to record in their eDiary daily	
Physician Global Assessment	X	X	X	X	X	X		X		
Partial Mayo Score		X	X	X	X				Include stool frequency, rectal bleeding, and physician's global assessment (PGA)	
Total Modified Mayo Score	X a					X		X	Include 4 components of stool frequency, rectal bleeding, endoscopy from Screening Period a , and PGA	
3-Component Modified Mayo Score	X a					X		X	Include 3 components of stool frequency, rectal bleeding, and endoscopy from Screening Period a	
IBDQ	X					X		X		
Laboratory Testing										
CBC	X		X			X		X		

	Study Visit							NOTES
	Study Week	0	2	6	10	12	Early Termination	
	Study Day	1	15	43	71	85		
Visit window (days)	0	±3	±3	±3	±3	±3		
Procedure								
Chemistry Panel	X		X			X	X	
Fasting Lipid Panel	X					X	X	
Urinalysis	X		X			X	X	
Urine Pregnancy Test (WOCBP only)	X		X			X	X	
Pharmacokinetics	X a	X b	X b	X b	X a	X	X	a. The PK samples at Week 0/Day 1 and Week 10 must be taken pre-dose, and immediately following the end of infusion (within 30 minutes) b. The PK sample taken at Weeks 2 and 6 must be taken pre-dose (within 30 minutes prior to dosing)
Pharmacokinetic Sub-Study (Optional)	X a				X a			a. In addition to the PK samples obtained in all subjects, PK sub-study subjects will have the following samples obtained: Week 0/Day 1 and Week 10: 4 days (96±5 hours) and 1 week (168±5 hours) after completion of infusion. Refer to Section 6.6.1 for additional details.
Immunogenicity	X	X	X	X		X	X	To be taken pre-infusion.
Biomarkers								
Biomarkers	X	X	X	X	X	X	X	Serum at all visits; additional whole blood at Weeks 0, 6, and 12
Soluble TL1A	X	X	X	X	X	X	X	
hsCRP	X	X	X	X	X	X	X	
Fecal Calprotectin	X			X		X	X	
Infusion	X	X	X	X	X			Include date, start and stop time, volume infused, and length of the IV infusion. Observation period at Week 0/Day 1 and Week 2 will be 1 hour (2 hours for subjects in Czech Republic); 30 minutes for all subsequent infusions thereafter.

**Table 3 Schedule of Study Assessments – Open-Label Extension Period for 1st Induction Responders**

	Study Visit										NOTES	
	Study Week	14	18	26	34	42	50	Quarterly (Q12w)* Office Visits after Week 50	Early Termination	Infusion Visits (excluding Office Visits)		
Study Day	99	127	183	239	295	351						Note: Subjects who are responders after the First Induction Period proceed to re-randomization at Week 14 *Weeks 62, 74, 86, 98, 110, 122, 134, 146, 158, and 170
Visit window (days)	±7	±7	±14	±14	±14	±14	±14					
Procedure												
Enter subject into IRT for OLE	X											
Complete Physical Examination						X		X a	X			a. Yearly after week 50
Targeted Physical Examination	X	X	X	X	X			X a				a. Except when the yearly complete exam is done
Vital Signs	X	X	X a	X	X	X a	X a		X a	X		Heart rate, temperature, blood pressure; Take pre-dose (no more than 30 minutes pre-infusion) and end of infusion a. Weight needed
EKG			X			X			X			
Adverse Events Assessment	X	X	X	X	X	X	X	X	X	X		
Concomitant Medication	X	X	X	X	X	X	X	X	X	X		
Efficacy Assessments												
Review Diary Data from Subjects	X	X	X	X	X	X	X	X	X	X		Electronic or paper diaries may be used
Physician Global Assessment	X	X	X	X	X	X	X	X	X	X		
Partial Mayo Score	X	X	X	X	X	X	X	X	X	X		Include stool frequency, rectal bleeding, and physician's global assessment (PGA)
Total Modified Mayo Score								X a	X	X		Include 4 components of stool frequency, rectal bleeding, endoscopy, and PGA a. Only if endoscopy is performed
3-component Modified Mayo Score								X a	X	X		Include 3 components of stool frequency, rectal bleeding, and endoscopy a. Only if endoscopy is performed
Endoscopy with Biopsy								X ab	X c	X c		Endoscopy can be performed 14 to 6 days prior to Week 50 and Week 98 visits or within 7 days after Week 50, Week 98, or ET visit

	Study Visit										NOTES	
	14	18	26	34	42	50	Quarterly (Q12w)* Office Visits after Week 50	Early Termination	Infusion Visits (excluding Office Visits)			
Study Week	14	18	26	34	42	50						Note: Subjects who are responders after the First Induction Period proceed to re-randomization at Week 14 *Weeks 62, 74, 86, 98, 110, 122, 134, 146, 158, and 170  a. For subjects who have had a diagnosis of UC for $\geq 7$ years and have been treated in OLE, the Week 50 and Week 98 endoscopies should also be a malignancy surveillance colonoscopy (rather than sigmoidoscopy). Refer to Section 6.4.2. b. Done annually (11-13 months from prior endoscopy) c. Required if $>3$ months since prior endoscopy  a. Every 6 months
Study Day	99	127	183	239	295	351	$\pm 14$			$\pm 7/\pm 14$		
Visit window (days)	$\pm 7$	$\pm 7$	$\pm 14$	$\pm 14$	$\pm 14$	$\pm 14$						
Procedure												
IBDQ			X			X	X a		X			
Laboratory Testing												
CBC	X	X	X	X	X	X	X		X			
Chemistry Panel	X	X	X	X	X	X	X		X			
Fasting Lipid Panel			X			X	X a		X			a. Every 6 months
Urinalysis	X	X	X	X	X	X	X a		X			a. Every 6 months
Urine Pregnancy Test (WOCBP only)	X	X	X	X	X	X	X		X			Pregnancy testing must be done once a month
Pharmacokinetics	X a		X a		X a	X a	X b		X			a. To be taken pre-infusion b. To be taken pre-infusion; every 6 months
Immunogenicity			X a		X a	X a	X b		X			a. To be taken pre-infusion b. To be taken pre-infusion; every 6 months
Biomarkers												
Biomarkers	X	X	X	X	X	X	X a		X			Additional whole blood at Week 50 and Week 98 a. Every 6 months
Soluble TL1A	X	X	X	X	X	X			X			
hsCRP	X	X	X	X	X	X	X a		X			a. Every 6 months
Fecal Calprotectin			X	X	X	X	X a		X			a. Every 6 months

	Study Visit										NOTES	
	14	18	26	34	42	50	Quarterly (Q12w)* Office Visits after Week 50	Early Termination	Infusion Visits (excluding Office Visits)			
Study Week	14	18	26	34	42	50						Note: Subjects who are responders after the First Induction Period proceed to re-randomization at Week 14 *Weeks 62, 74, 86, 98, 110, 122, 134, 146, 158, and 170
Study Day	99	127	183	239	295	351						
Visit window (days)	±7	±7	±14	±14	±14	±14	±14		±7/±14			
Procedure												
Infusion	X	X	X	X	X	X	X		X a			a Q4 week infusion visits Include date, start and stop time, volume infused, and length of the IV infusion Infusion observation period will be 30 minutes

**Table 4 Schedule of Study Assessments – Open-Label Extension Period for 1st Induction Non-Responders**

Study Week	Study Visit										NOTES	
	14	16	20	24	26	28	36	44	48	Quarterly (Q12w)* Office Visits after Week 48		Early Termination
Study Day	99	113	141	169	183	197	253	309	337			
Visit window (days)	±7	±7	±7	±7	±14	±14	±14	±14	±14	±14		±7/±14
Procedure												
Enter subject into IRT for OLE					X							
Complete Physical Examination									X	X a	X	
Targeted Physical Examination	X	X	X	X	X	X	X	X		X a		
Vital Signs	X	X	X	X	X a	X	X	X	X a	X a	X a	X
ECG					X				X		X	
Adverse Events Assessment	X	X	X	X	X	X	X	X	X	X	X	X
Concomitant Medication	X	X	X	X	X	X	X	X	X	X	X	X
Efficacy Assessments												
Review Diary Data from Subjects	X	X	X	X	X	X	X	X	X	X	X	
Physician Global Assessment	X	X	X	X	X	X	X	X	X	X	X	
Partial Mayo Score	X	X	X	X	X	X	X	X	X	X	X	
Total Modified Mayo Score									X	X a	X	
3-component Modified Mayo Score									X	X a	X	

Note: Subjects showing a response after second induction per Investigator discretion should proceed to re-randomization at Week 28

\*Weeks 60, 72, 84, 96, 108, 120, 132, 144, 156 and 168

Applicable for non-responders who complete second induction

Subject Response is registered as part of Week 28

a. Yearly after Week 48

a. Except when the yearly complete exam is not done

Heart rate, temperature, blood pressure; Take pre-dose (no more than 30 minutes pre-infusion) and end of infusion

a. Weight needed

Electronic or paper diaries may be used

Include stool frequency, rectal bleeding, and physician's global assessment (PGA)

Include 4 components of stool frequency, rectal bleeding, endoscopy, and PGA

a. Only if endoscopy is performed

Include 3 components of stool frequency, rectal bleeding, and endoscopy

a. Only if endoscopy is performed

Study Week	Study Day	Visit window (days)	Study Visit										NOTES		
			14	16	20	24	26	28	36	44	48	Quarterly (Q12w)* Office Visits after Week 48		Early Termination	Infusion Visits (excluding Office Visits)
		±7	±7	±7	±7	±7	±14	±14	±14	±14	±14	±14		±7/±14	Note: Subjects showing a response after second induction per Investigator discretion should proceed to re-randomization at Week 28 *Weeks 60, 72, 84, 96, 108, 120, 132, 144, 156 and 168
Procedure															
Endoscopy with Biopsy															Endoscopy can be performed ≤14 to ≥6 days prior to Week 48 and Week 96 visits or within 7 days after Week 48, Week 96, or ET visit a For subjects who have had a diagnosis of UC for ≥ 7 years and have been treated in OLE, the Week 48 and Week 96 endoscopies should also be a malignancy surveillance colonoscopy (rather than sigmoidoscopy). Refer to Section 6.4.2. b Done annually
IBDQ							X					X a			a Every 6 months
Laboratory Testing															
CBC			X	X	X		X	X	X	X	X	X			
Chemistry Panel			X	X	X		X	X	X	X	X	X			
Fasting Lipid Panel							X					X a			a Every 6 months
Urinalysis			X	X	X		X	X	X	X	X	X a			a Every 6 months
Urine Pregnancy Test (WOCBP only)			X	X	X		X	X	X	X	X	X		X	Pregnancy testing must be done once a month
Pharmacokinetics			X a	X a			X a	X a	X a	X a	X a	X b			a To be taken pre-infusion b To be taken pre-infusion; every 6 months
Immunogenicity				X a			X a	X a	X a	X a	X a	X b			a To be taken pre-infusion b To be taken pre-infusion; every 6 months
Biomarkers															
Biomarkers			X	X	X		X	X	X	X	X	X a			Additional whole blood at Week 48 and Week 96 a Every 6 months

	Study Visit											NOTES		
	14	16	20	24	26	28	36	44	48	Quarterly (Q12w)* Office Visits after Week 48	Early Termination		Infusion Visits (excluding Office Visits)	
Study Week	14	16	20	24	26	28	36	44	48					Note: Subjects showing a response after second induction per Investigator discretion should proceed to re-randomization at Week 28 *Weeks 60, 72, 84, 96, 108, 120, 132, 144, 156 and 168
Study Day	99	113	141	169	183	197	253	309	337					
Visit window (days)	±7	±7	±7	±7	±14	±14	±14	±14	±14	±14			±7/±14	
Procedure														
Soluble TL1A	X	X	X		X	X	X	X	X				X	
hsCRP	X	X	X		X	X	X	X	X	X a			X	a Every 6 months
Fecal Calprotectin		X			X	X	X	X	X	X a			X	a Every 6 months
Infusion														a Q4 week infusion visits Include date, start and stop time, volume infused, and length of the IV infusion Infusion observation period will be 30 minutes
	X	X	X	X		X	X	X	X	X			X a	

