## 6 STUDY PROCEDURES

A schedule of study procedures is presented in [Section 6.1.1](#). If any discrepancies should be found between the text of the protocol and the Schedule of Study Assessments tables, the tables will predominate.

Every effort should be made to ensure that the protocol-required tests and procedures are completed as described. However, it is anticipated that from time to time there may be circumstances, outside of the control of the Investigator that may make it unfeasible to perform the test. In these cases, the Investigator will take all steps necessary to ensure the safety and well-being of the subject. When a protocol-required test cannot be performed, the Investigator will document the reason for this and any corrective and preventive actions that he or she has taken to ensure that normal processes are adhered to as soon as possible. The Sponsor or designee will be informed of these incidents in a timely fashion.

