## 6.2 Other Information for Study Visits

Unscheduled procedures may be required in addition to the procedures detailed above for subject safety and/or exacerbation assessments. The additional procedures are at the discretion of the Investigator. The details of these unscheduled procedures will be recorded in the source documents and entered into the eCRFs.

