## 6.3 Safety Assessment Description

### 6.3.1 Medical History, Physical Examination, Height and Weight

Medical history, including UC history, will be collected at the Screening Visit.

The Investigator will perform a complete physical examination at the Screening Visit and at the at the Week 12/Early Termination (ET), Week 50/ET, and yearly thereafter, at a minimum. The complete physical examination must include the following:

- General appearance
- Hair and skin
- Lymph nodes
- Head
- Eyes
- Ears, nose, and throat
- Neck
- Respiratory
- Cardiovascular
- Abdominal
- Musculoskeletal
- Mental status
- Neurological

Unless otherwise indicated, following screening visit, physical examinations should be targeted (symptom directed). Complete and targeted physical examinations are to be performed at specified timepoints according to the schedule of study procedures ([Section 6.1.1](#)).

Height and weight will be measured without the subject wearing shoes. Height (inches or centimeters) will be measured and recorded at the screening visit only and weight (lbs or kg) will be measured and recorded at various timepoints ([Section 6.1.1](#)).

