#### **6.4.1 Modified Mayo Scoring System**

The Modified Mayo Scoring system will be reviewed and discussed with the investigational staff at the Investigators' Meeting or other forum as a method of standardizing the grading between the investigational staff. For each of the visit where partial Mayo score or 3-component Modified Mayo score/Total Modified Mayo score is collected, subject should complete the eDiary or paper diary entries at least 7 days immediately preceding each study visit.

The eDiary/paper diary will collect the following information on a daily basis during the study:

- ‘Normal’ number of stools per day (when not having a flare). This question will be asked only at the screening visit.
- Number of times needed to visit the toilet to have a bowel movement (per day).
- Presence of blood in the stools (if any).
- Description of blood in the stools (if any).

eDiary/paper diary entries completed by the subject from the most recent **3 consecutive** evaluable days (or the most recent **4 non-consecutive** evaluable days, if there are no 3 consecutive evaluable days available) during the preceding 7 days prior to the visit will be used to calculate the Mayo score. For Day 1/Week 0, subject should not be randomized unless there are adequate evaluable symptom days (3 consecutive evaluable days or 4 non-consecutive evaluable days during the preceding 7 days). Note that symptoms on days of the bowel preparation, endoscopy, and 2 days post endoscopy are not considered evaluable.

Each subject serves as their own control to establish the degree of abnormality of stool frequency. The physician’s global assessment acknowledges the three other criteria (i.e., stool frequency, rectal bleeding, and endoscopy subscore where Mayo score is required), the subject’s daily recollection of number of stools per day and presence of blood in the stools, as well as other observations, such as physical findings and subject’s performance status.

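### A stray 'not' in Table 4 reverses the rule for targeted physical examinations after Week 48 in the non-responder extension schedule (minor drafting error)

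*Protocol*

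**What the plan says.** Section 6.1.1 has separate extension schedules for first-induction responders (Table 3) and non-responders (Table 4). Both have one row for the complete physical examination and one for the targeted examination. In both, the quarterly-visit column carries a footnote on each of these rows.

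- **Complete examination:** yearly, after Week 50 in Table 3 and after Week 48 in Table 4.
- **Targeted examination, Table 3:** "Except when the yearly complete exam is done".
- **Targeted examination, Table 4:** "Except when the yearly complete exam is not done".

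Section 6.3.1 makes examinations after screening symptom-directed by default. It asks for complete examinations at "Week 50/ET, and yearly thereafter, at a minimum", and leaves the timing to the schedule: "Complete and targeted physical examinations are to be performed at specified timepoints according to the schedule of study procedures". Section 6 adds: "If any discrepancies should be found between the text of the protocol and the Schedule of Study Assessments tables, the tables will predominate".

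**The concern.** The Table 4 note waives the targeted examination at exactly the visits where no complete examination takes place, and keeps it where a complete examination already covers it. Table 3 does the reverse, for the same assessment at the same kind of visit.

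Subjects who failed the first induction, responded to the second and stayed past Week 48 would then lose most of their scheduled physical examinations, while responders kept theirs. The synopsis gives long-term safety data as the reason for lengthening the extension, and Section 8.3 lists physical examination among the safety variables. The slip therefore runs against the purpose of this period.

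**Working it through.** **1. Which row the note belongs to.** In the available text of Table 4 the notes are detached from the grid. Their order is: yearly after Week 48 (complete examination), then the note in question, then the vital-signs note. Table 3 prints the same sequence attached to its rows. In Table 4 both examination rows carry superscript a in the quarterly column. The note therefore belongs to the targeted-examination row.

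**2. Table 4 against its own grid.**

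| Visits | Targeted | Complete |
|---|---|---|
| Weeks 14, 16, 20, 24, 26, 28, 36, 44 | yes | no |
| Week 48 | no | yes |
| Quarterly, note as written, yearly visit | yes | yes |
| Quarterly, note as written, other visits | no | no |
| Quarterly, 'not' deleted, yearly visit | no | yes |
| Quarterly, 'not' deleted, other visits | yes | no |

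Up to Week 48 each visit has one examination or the other. Only the reading without 'not' continues that pattern.

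**3. Visits affected on the literal reading.** Table 4 lists quarterly visits at Weeks 60, 72, 84, 96, 108, 120, 132, 144, 156 and 168, which makes 10. It does not say which of them carry the yearly complete examination, so a placement has to be assumed.

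- Take Section 6.3.1's yearly minimum as an interval of no more than 52 weeks. On a 12-week grid the longest such interval is 4 × 12 = 48 weeks, because 5 × 12 = 60 exceeds a year.
- Counting from Week 48: 48 + 48 = 96 and 96 + 48 = 144. The next would be Week 192, after the last visit.
- One complete examination would not be enough. It would have to fall no later than 48 + 52 = Week 100 and no earlier than 168 − 52 = Week 116, which is impossible. Two is the minimum.
- The step from Week 48 to Week 96 matches the endoscopy timing in the same table: "the Week 48 and Week 96 endoscopies should also be a malignancy surveillance colonoscopy".

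Visits with no scheduled examination are then Weeks 60, 72, 84, 108, 120, 132, 156 and 168, that is 10 − 2 = 8 of 10. Scheduled examinations fall at Weeks 48, 96 and 144, 48 weeks apart, with none in the 24 weeks from Week 144 to Week 168.

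**4. Sensitivity to placement.** Reading yearly more loosely, complete examinations at Weeks 96 and 156 give intervals of 48 and 60 weeks, with 12 weeks left to Week 168. Weeks 108 and 168 give intervals of 60 and 60. The count stays at 8 of 10 in each case; the spacing changes.

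**5. With 'not' deleted.** All 10 visits have an examination (8 targeted and 2 complete on the same assumption), 12 weeks apart.

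**6. Whether other columns fill the gap.** Table 4's infusion-only visits and the follow-up visits in Table 5 schedule no physical examination. The early-termination visit does include a complete one.

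**The case against.** The best reply is that this is a typographical error that no competent site would follow. The literal rule makes no sense, the grid and Table 3 both show the intent, and Section 6.3.1 makes targeted examinations the default. That is largely right, and it is why the point is minor.

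Two narrower objections also have force. First, the precedence rule in Section 6 ranks tables over text and does not rank one table over another, so it does not make Table 4 prevail over Table 3. It does mean that the default in Section 6.3.1 cannot formally override the footnote, and that section hands timing back to the schedule anyway. Second, the protocol does not fix complete examinations at Weeks 96 and 144, and the yearly wording in Section 6.3.1 is tied to Week 50, which is not a Table 4 visit. The 48-week spacing therefore depends on an assumption. The count of 8 requires only that there be two yearly examinations.

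Other safeguards remain. Adverse event assessment, vital signs with weight, blood count, chemistry and the physician's global assessment are all scheduled at the quarterly visits. According to Section 6.4.1 the global assessment considers symptoms and scores "as well as other observations, such as physical findings". Section 6.2 states: "Unscheduled procedures may be required in addition to the procedures detailed above for subject safety and/or exacerbation assessments".

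**Conclusion.** The concern holds, as a minor drafting error and not a design decision. The Table 4 footnote is wrong as written, and no other provision formally corrects it. On the literal reading, and assuming two yearly complete examinations between Weeks 60 and 168, 8 of 10 quarterly visits have no scheduled physical examination. The intervals are 48 weeks if those examinations fall at Weeks 96 and 144, against 12 weeks as evidently intended.

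The documents do not allow the number of subjects affected to be derived, and they give no evidence that any site would apply the note literally. Under Section 9.3.7.2 examination data are listed by subject and changes are described in the report, so no efficacy or comparative analysis is affected, nor is the sample size or alpha.

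**What to change.** Delete 'not' from the Table 4 footnote so that it matches Table 3: "Except when the yearly complete exam is done". Make the change in the next routine amendment and send sites a short clarification in the meantime. The cost is one word and one notice, with no visits or procedures beyond those evidently intended.
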